12.2.5 Treatment of Adverse Events

AEs that may be related or possibly related to a drug with immune modulation mechanisms of action may include anaphylactic reaction or acute pro-inflammatory cytokine release.

- Management of anaphylaxis should follow appropriate guidelines and recommendation such as those made by the Resuscitation Council of New Zealand, 2006
- Acute pro-inflammation should be treated with appropriate fluid replacement, anti-inflammatory drugs (steroidal and non-steroidal) and antihistamines.

12.2.6 Causality Assessment

The Investigator's assessment of causality must be provided for all AEs (serious and nonserious). An investigator's causality assessment is the determination of whether there exists a reasonable possibility that the investigational product caused or contributed to an AE. For this assessment, investigators must categorize the causality as unrelated, possibly related, probably related or related according to the following definitions:

Unrelated: There is evidence that the AE definitely has an etiology other than the assigned study drug.

Version 5

- **Possibly Related:** The adverse event has a temporal relationship to study drug administration. However, an alternative etiology may be responsible for the AE. Information on drug/product withdrawal may be lacking or unclear.
- **Probably Related:** The AE has a temporal relationship to study drug administration. The event is unlikely to be related to an alternative etiology. There is a reasonable response on withdrawal (dechallenge).
- **Related:** The adverse event has a temporal relationship to study drug administration and resolves when the drug is discontinued. An alternative etiology is not apparent.

12.2.7 Follow-up of Adverse Events

AEs, especially those for which the relationship to study drug is not "unrelated", should be followed-up until they return to baseline status or stabilised. If a clear explanation is established it should be recorded on the CRF.

In the event of unexplained clinically relevant abnormal laboratory test values, the tests should be repeated immediately and followed-up until they have returned to the normal range and/or an adequate explanation of the abnormality is found. If a clear explanation is established, it should be recorded on the CRF.

12.2.8 Pregnancy

Pregnancy occurring in the partner of a subject participating in the study, if the investigator becomes aware of it, should also be reported to the sponsor within 24 hours. A Pregnant Partner Consent Form is provided to document discussions with the partner of the study participant and to obtain her consent to collect follow up information regarding the pregnancy. The partner should be counseled regarding the possible effects to the fetus and monitoring of the subject should continue until conclusion of the pregnancy, where consent to do so is given.

13. Criteria for Premature Withdrawal

Subjects have the right to withdraw from the study at any time for any reason.

The investigator also has the right to withdraw subjects from the study in the event of intercurrent illness, AEs, protocol violations, administrative reasons or other reasons.

Should a subject decide to withdraw, all efforts should be made to complete and report the follow-up procedures, particularly the physical examination, as thoroughly as possible.

Version 5

Subjects who have prematurely withdrawn may be replaced, at the discretion of the investigators and with the approval of the sponsor, if withdrawal occurs for reasons other than DLT or an SAE related to study drug.

14. Statistical Considerations

The statistical analysis plan and biostatistical analysis is provided by Westat (Houston, TX).

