4.4 Dose Limiting Toxicity (DE phase only)

A DLT is a clinically significant adverse event (AE) or laboratory abnormality assessed by the Co-Principal Investigators as at least possibly related to the study drug and unrelated to disease progression, concurrent illness, or concomitant medications, occurring within Cycle 1. Toxicity will be graded and recorded according to the Toxicity Grading Scale for Healthy Adult and Adolescent Volunteers Enrolled in Preventative Vaccine Clinical Trials (presented in the companion Operations Manual), modified to include a systemic line item for rigors/chills and an amendment to the classification of pyrexia (Appendix 3). A DLT is defined as:

- Grade 3 or 4 adverse event, except for fatigue and fever and/or rigors/chills
- Grade 4, or an increase above baseline of 2 or more grades, fatigue
- Grade 4 fever and/or rigors/chills.

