4.5 Dose Confirmation Phase (up to total of 3 cycles)

The DC phase will not begin until the Sponsor has submitted to the Ethics Committee and regulatory authority the requisite sub-chronic nonclinical safety data, and received approval to proceed to 3 cycles of dosing.

In the DC phase, up to 15 subjects will be recruited at the RP2D. The Safety Team will have the responsibility of reviewing safety data from the DC phase of the trial and making recommendations regarding dose modifications. If a DC phase subject withdraws from dosing within the first 2 cycles for reasons unrelated to drug toxicity, the subject may be replaced at the discretion of the Safety Review Team.

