14.2.2 Safety Evaluable (SE) Population

The SE population consists of subjects receiving any amount of MIS416. The estimation of toxicity rates will be based on the SE population.

Version 5

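### Replacement of withdrawn subjects: Section 13 contradicts Section 4.5 in the dose-confirmation phase, and in the dose-escalation phase the any-dose denominator counts incompletely observed, replaced subjects as DLT-free

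*Protocol*

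**What the plan says.** **Replacement, general rule (Section 13).** A new subject may take the place of one who has left early "if withdrawal occurs for reasons other than DLT or an SAE related to study drug". The investigators decide, and the sponsor has to agree. There is no time limit and no restriction to one phase. The same section foresees that the investigator may withdraw subjects for adverse events generally.

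**Replacement, DC phase (Section 4.5; same wording in the synopsis).** The rule covers a DC subject who "withdraws from dosing within the first 2 cycles for reasons unrelated to drug toxicity"; in that case "the subject may be replaced at the discretion of the Safety Review Team".

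**What a DLT is (Section 4.4).** DLTs are defined for the DE phase only. The first criterion is "Grade 3 or 4 adverse event, except for fatigue and fever and/or rigors/chills". Fever and rigors/chills become DLTs only at Grade 4.

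**Observation and counting (Section 4.3).** Escalation is decided on 3 or 6 subjects per dose. A new level may open only when all subjects at the current level have been followed for at least 7 days after their fourth dose.

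**Denominator (Section 14.2.2).** The safety-evaluable (SE) population is anyone given any amount of MIS416, and "The estimation of toxicity rates will be based on the SE population".

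**The concern.** In the DC phase two rules govern the same event and give different answers. Section 2.3 says this phase exists to build a safety database at the selected dose, so it matters whether subjects who stop for drug toxicity are replaced: that decides who makes up the cohort of up to 15. It also matters who decides. The Safety Review Team includes an independent clinical expert (Section 4.8), whom the Section 13 route bypasses.

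In the DE phase only Section 13 applies. A subject who stops after one or two infusions without a DLT can be replaced, yet has not been observed for the period on which the DLT decision rests. The SE denominator nevertheless counts that subject as if fully observed and free of DLT. Fever and chills are the reactions the protocol expects from the drug (Sections 1.4.5 and 2.1), and at Grade 3 they are not DLTs, so such a stop is not far-fetched. Safety, tolerability and the MTD are primary objectives.

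**Working it through.** **1. The two replacement rules side by side, for a DC subject**

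| Item | Section 13 | Section 4.5 and synopsis |
|---|---|---|
| Reasons allowed | Anything but a DLT or a related SAE | Only reasons unrelated to drug toxicity |
| Time limit | None | First 2 cycles |
| Who decides | Investigators, with sponsor approval | Safety Review Team |

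Since DLTs are defined only for the DE phase, a drug-related SAE is the only bar that Section 13 sets in the DC phase. A subject who stops for non-serious drug toxicity is therefore replaceable under Section 13 and not under Section 4.5. The synopsis does use the term DLT once in its DC dose-reduction paragraph, but applying the DLT criteria there would not remove the conflict: Grade 3 fever or rigors would still not be a DLT.

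*Effect on a DC rate.* Assume r = 1 to 5 toxicity stops (the protocol gives no figure), all replaced, with no replacement subject stopping. The SE rate of such stops is r/(15 + r), from 1/16 to 5/20 (6% to 25%). Without replacement it is r/15, from 1/15 to 5/15 (7% to 33%).

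**2. The protocol's own escalation table (Section 14.1)**

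Under the 3+3 rule with true DLT rate p, P(escalate) = (1−p)³ + 3p(1−p)² × (1−p)³. At p = 0.30 this is 0.343 + 0.441 × 0.343 = 0.494, against the stated 49%. From p = 10% to 90% the formula gives 90.6, 70.9, 49.4, 30.9, 17.2, 8.2, 3.2, 0.9 and 0.1%, so all nine entries reproduce. The calculation takes exactly 3 or 6 counted subjects per dose. The protocol does not say whether an early stopper, or the replacement, is one of them.

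**3. Effect of the SE denominator on a DE DLT rate**

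Let d be DLTs, n the fully observed or DLT subjects, and r the subjects treated, stopped without a DLT and replaced. The rate on the SE set is d/(n + r) instead of d/n. With r = 1 to 3 per cohort (assumed):

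| d/n | r = 1 | r = 2 | r = 3 |
|---|---|---|---|
| 1/3 (33%) | 1/4 (25%) | 1/5 (20%) | 1/6 (17%) |
| 1/6 (17%) | 1/7 (14%) | 1/8 (13%) | 1/9 (11%) |
| 2/6 (33%) | 2/7 (29%) | 2/8 (25%) | 2/9 (22%) |

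**The case against.** **Section 4.5 is the specific rule, Section 13 the general one, and both are discretionary.** A careful reader might let the specific rule prevail for DC subjects. But the protocol does not state that precedence, and the two name different decision-makers, so a site could follow either in good faith.

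**The MTD is decided on counts, and no DLT-rate table is promised.** This stands. Two DLTs end escalation whatever the denominator. Section 14.5.3 promises toxicity rates, and Section 14.5.3.2 identifies DLTs in listings. The dilution therefore affects a descriptive rate. It could reach the dose decision only through the unanswered question of who counts in the 3 or 6.

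**The analysis plan may define an evaluable set.** It may, but the protocol is not silent on the denominator: it fixes the SE population for toxicity rates.

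**Stronger readings the documents do not support.**
- A reader might infer that intolerance drops out of sight. It does not. Withdrawn subjects stay in the final safety analysis (Section 5.1), discontinuations for adverse events are presented (Section 14.5.3.2), as are reasons for early termination (Section 14.5.1), and the Safety Review Team reviews all available safety data before each escalation (Section 4.8).
- A reader might infer that replacement makes escalation more likely. Let q be the probability of a non-DLT toxicity stop (assumed 10% to 30%) and take p = 20%. Keeping such subjects as non-DLTs gives P(escalate) = 71%; replacing them, with p/(1−q) in the formula, gives 66% to 52%. Escalation is more likely only when compared with counting the stop as a DLT (p + q in the formula: 49% to 17%), which the protocol does not do.
- A reader might link the two defects causally. They are separate: Section 4.5 does not govern the DE phase, and DLTs are not defined for the DC phase.

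**Conclusion.** The point holds as two separate defects of moderate weight.

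- **DC phase:** Sections 13 and 4.5 (with the synopsis) contradict each other on reason, time limit and decision-maker. This follows from the text alone and needs no assumption.
- **DE phase:** any DLT rate on the SE population is pulled down by replaced subjects who were not fully observed, for example from 33% to between 29% and 22% for two DLTs in six. That size rests on an assumed 1 to 3 replacements per cohort; with none there is no dilution. The membership of the 3 or 6 is also left open.

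Neither defect shows that the MTD would be wrong or that toxicity would go unreported.

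**What to change.** 1. **DC phase:** reconcile Section 13, Section 4.5 and the synopsis into one replacement rule that states reasons, time limit and decision-maker. One simple edit is to make Section 13 defer to Section 4.5 for DC subjects.
2. **DE phase, analysis set:** define a DLT-evaluable set, meaning subjects who had a DLT, or who received all four doses and were observed for 7 days after the last. Use it for the 3+3 count and for DLT rates. Keep the SE population for all other safety tables.
3. **DE phase, counting:** state that a subject who is not DLT-evaluable is replaced in the 3 or 6. State also that a stop for drug-related toxicity short of a DLT is put to the Safety Review Team before it decides on escalation. Without these two sentences such a subject would be neither evaluable nor clearly replaceable.
4. **Reporting:** tabulate replaced subjects and their reasons by dose, over all treated subjects.

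The cost is some wording, one definition and one table. The downside is that a cohort may take slightly longer to complete.

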14.1 Sample Size and Determination of MTD

There are no formal statistical calculations to determine the sample size. The total number of subjects to be enrolled in the study is dependent upon the observed safety profile, which will determine the number of subjects per dose level, as well as the number of dose escalations required to achieve the MTD. It is anticipated that approximately 27-33 subjects will be enrolled, with approximately 12-18 subjects in the dose-escalation phase and up to additional 15 subjects in the dose-confirmation phase.

The table below gives the probabilities of dose escalation at any stage during the MTD determination, as a function of the true, but unknown underlying DLT rate at the current dose level.

| Underlying DLT rate | 10% | 20% | 30% | 40% | 50% | 60% | 70% | 80% | 90% |
|--------------------------------|-----|-----|-----|-----|-----|-----|-----|-----|------|
| Probability of dose escalation | 91% | 71% | 49% | 31% | 17% | 8% | 3% | 1% | 0.1% |

14.2 Analysis Populations

14.2.1 Intent-to-Treat (ITT) Population

All subjects who were screened and met the eligibility requirements, regardless of their compliance with the treatment per protocol will be in the ITT analysis. A subject may have baseline measurements, but may not receive treatment or have any follow-up data. However, this subject will be part of the analysis.

14.2.2 Safety Evaluable (SE) Population

The SE population consists of subjects receiving any amount of MIS416. The estimation of toxicity rates will be based on the SE population.

Version 5

14.2.3 Clinical Status (CS) Population

The CS population includes subjects who have been on the trial for at least 2 months and have had end-of-Cycle 2 clinical status assessments recorded.

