2.3 Rationale Dose-Confirmation Phase

Once such dose selection occurs, the intent of the dose-confirmation phase of this trial is to create a safety database sufficient to support longer-term exposure in the planned efficacy trial. This will be accomplished by (a) expanding the patient population exposed to this dose level and (b) prolonging exposure to 3 months. This will allow confirmation of the longer-term safety and tolerability of MIS416 before exposing a much larger population to a lengthier dosing regimen in the planned efficacy trial. Given the variable but generally progressive nature of multiple sclerosis, patients treated for 3 months will be observed closely not only for standard safety outcomes but also for changes in underlying disease status – both to rule out any adverse effect of MIS416 on disease progression and to document any anecdotal changes that may inform the selection of patients and/or endpoints for the initial efficacy trial.

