14.3 Data Handling

14.3.1 Measurement Times

14.3.1.1 Visit Windows

Visit windows will not be used. The nominal visit time point entered on the case report forms will be used. Unscheduled assessments, if any, will be listed, but will not be included in tabulations by visit.

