14.3.2 Missing Data Conventions

Unless otherwise specified, missing data will be considered missing at random and will not be imputed. However, imputation of partial dates may be performed during the data analysis and will be documented.

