14.5.4 Analysis of Clinical Status

Analyses of clinical status endpoints will be conducted on the CS population. Summary statistics will be presented for baseline measurements and changes from baseline at each dose level for the following:

- MSFC score
- FSS score
- SF-36 score
- EDSS score
- Self-reported and clinically confirmed clinical exacerbations

Time to EDSS (TTE) deterioration will be determined as follows:

Date of first of two confirmed deteriorations from baseline minus Date of 1^{st} Study Drug Administration + 1 day. TTE deterioration will be calculated in days, but will be reported in days or months.

Version 5

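### The clinical-status measures are analysed only in subjects retained for two months, so a dose-confirmation subject who worsens and leaves early drops out of those summaries and may be replaced

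*Protocol*

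**What the plan says.** All references are to the Protocol.

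- **Purpose.** Section 2.3 says disease status is followed over three months in the DC phase partly "both to rule out any adverse effect of MIS416 on disease progression". The Synopsis makes it a secondary objective to document changes in clinical status over the 12-week dosing period of that phase.
- **Analysis set.** Section 14.5.4: "Analyses of clinical status endpoints will be conducted on the CS population". It lists MSFC, FSS, SF-36, EDSS and exacerbations, and defines time to EDSS deterioration.
- **Who is in the set.** Section 14.2.3: the CS population "includes subjects who have been on the trial for at least 2 months and have had end-of-Cycle 2 clinical status assessments recorded".
- **Replacement.** Section 4.5: "If a DC phase subject withdraws from dosing within the first 2 cycles for reasons unrelated to drug toxicity, the subject may be replaced". The decision rests with the Safety Review Team. Section 13 allows replacement of prematurely withdrawn subjects "if withdrawal occurs for reasons other than DLT or an SAE related to study drug". Neither rule mentions worsening of MS.
- **Data at early exit.** Section 6.5.2 and Tables 3 and 4 schedule EDSS, MSFC, FSS, SF-36 and cranial MRI at Early Discharge.
- **Missing data.** Section 14.3.2: "missing data will be considered missing at random and will not be imputed", unless otherwise specified.
- **All-dosed summaries.** Section 14.5.3 puts safety analyses, including adverse events (14.5.3.2) and MRI (14.5.3.6), on the Safety Evaluable population, meaning anyone given any amount of MIS416. Section 12.2.1 makes worsening of a pre-existing condition a reportable adverse event.

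**The concern.** Entry to the CS population is decided by what happens after dosing, and what happens may be the outcome itself. A subject whose MS worsens in weeks 1 to 8 and who stops has assessments at exit, but the plan does not use them for clinical status. With no imputation, nothing puts that subject back. If the worsening is attributed to MS rather than to the drug, the replacement rules allow the place to be filled by someone else, who may enter the CS set.

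At stake is whether the clinical-status tables describe the people who were dosed or only those who stayed. The study has one arm, so no comparison group would show the selection. Section 2.3 says what is learned here may inform the choice of patients and endpoints for the efficacy trial.

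**Working it through.** The protocol gives no worsening rate, no early-exit rate and no calculation for this analysis, so there is no stated figure to reproduce. From the documents come the size of the DC phase (up to 15), the CS rule, the replacement rules and the visit schedule. Every rate and count of worseners below is an assumption.

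**Step 1. When a subject qualifies.** No visit is labelled end of Cycle 2. The nearest scheduled EDSS, MSFC and FSS are on Day 1 of Cycle 3 (Section 6.4, Table 4). With 28-day cycles that is Day 2 × 28 + 1 = 57. In practice a subject must stay about eight weeks.

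**Step 2. What happens to an early worsener.** Take a DC subject who worsens, stops before that visit and attends Early Discharge:

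| Route | Worsening attributed to MS | Worsening attributed to drug toxicity |
|---|---|---|
| Clinical-status summaries (14.5.4) | Excluded | Excluded |
| Replacement (4.5) | Allowed, discretionary | Not allowed |
| Adverse-event and MRI summaries (14.5.3) | Included | Included |

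The exclusion does not depend on attribution. Replacement under Section 4.5 does.

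**Step 3. Effect in counts.** Assume 15 DC places. Suppose k subjects worsen, leave early and are replaced, while the other 15 neither worsen nor leave early. The CS result is 0/15 for every k. Over all dosed subjects the proportion is k/(15 + k), with exact (Clopper-Pearson) 95% intervals:

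| k | CS set | All dosed DC subjects | 95% CI |
|---|---|---|---|
| 1 | 0/15 | 1/16 = 6.3% | 0.2 to 30.2% |
| 2 | 0/15 | 2/17 = 11.8% | 1.5 to 36.4% |
| 3 | 0/15 | 3/18 = 16.7% | 3.6 to 41.4% |
| 4 | 0/15 | 4/19 = 21.1% | 6.1 to 45.6% |

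Replacement is not needed for the effect. With k = 3 and no replacement, the CS set shows 0/12 against 3/15 = 20.0% (4.3 to 48.1%) of all dosed.

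**Step 4. Effect in expectation, and its direction.** Let p be the true proportion who worsen, f the share of worseners who leave before the end-of-Cycle 2 assessment, and g the same share among non-worseners. The expected CS rate is

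p(1 − f) / [p(1 − f) + (1 − p)(1 − g)].

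With g = 0 this is p(1 − f)/(1 − pf):

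| p | f = 25% | f = 50% | f = 75% |
|---|---|---|---|
| 10% | 7.7% | 5.3% | 2.7% |
| 20% | 15.8% | 11.1% | 5.9% |
| 30% | 24.3% | 17.6% | 9.7% |

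At p = 20% and f = 50%, the chance of seeing no worsening in 15 CS subjects is (1 − 0.111)^15 = 17.1%, against 0.8^15 = 3.5% in 15 unselected subjects.

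The direction depends on g. Keep p = 20% and f = 50%:

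- g = 0: 0.10/(0.10 + 0.80) = 11.1%, an understatement.
- g = 50%: 0.10/(0.10 + 0.40) = 20%, no bias.
- g = 75%: 0.10/(0.10 + 0.20) = 33.3%, an overstatement.

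The summaries therefore understate worsening only when f exceeds g.

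**The case against.** The strongest reply is that the trial has other ways to see worsening. It must be reported as an adverse event. Adverse events, discontinuations due to them and MRI changes are summarised in all dosed subjects, reasons for early termination are tabulated on the ITT population, and the Safety Review Team oversees safety in the DC phase. The objective is secondary and descriptive, there is no hypothesis test, and an unseen analysis plan could add an all-dosed summary.

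Most of that stands and limits the point. What remains is that an adverse-event count is not a change in EDSS, MSFC, FSS or SF-36. The protocol fixes the population for those measures instead of leaving it open, and the ITT clinical-status summary in Section 14.5.2.3 covers baseline characteristics only.

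A reader might go further in five ways that the documents do not support:

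- **That harm to disease course cannot be looked for at all.** The adverse-event and MRI routes remain, and Section 2.3 speaks of close observation without naming the CS tables as the means.
- **That leaving out dose-escalation subjects is a defect.** The Synopsis restricts this objective and analysis to the DC phase.
- **That time to EDSS deterioration has a two-month immortal period.** CS members can deteriorate in the first two months, and the clock starts at first dose. The fault is selection on retention.
- **That unscheduled EDSS values are discarded.** Section 14.3.1.1 says: "Unscheduled assessments, if any, will be listed, but will not be included in tabulations by visit". That does not bar them from time to deterioration or exacerbation counts.
- **That the upper limit of 21.8% for 0/15 shows the harm of the CS rule.** Any unselected 15 subjects with no events give the same limit. It reflects sample size.

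**Conclusion.** The point holds in a limited form and should be fixed. Followed as written, Sections 14.2.3 and 14.5.4 exclude collected clinical-status data on any DC subject who leaves before the end-of-Cycle 2 assessment, and Sections 4.5 and 13 allow such a subject to be replaced when worsening is attributed to MS. That much follows from the text.

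The size does not. In the illustration, one to four replaced worseners separate 0/15 from 6% to 21% of all dosed subjects, but those counts are assumed. The bias is toward less worsening only if worseners leave more often than others. It vanishes if both leave equally often and reverses if non-worseners leave more.

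The loss is confined to the clinical-status analysis. It touches neither dose selection nor the adverse-event and MRI summaries.

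**What to change.** - Make the main clinical-status set all DC subjects who received any MIS416 and have a baseline value, with the Early Discharge assessment as the last value for those who leave.
- Count exacerbations and EDSS deterioration from first dose over all dosed DC subjects.
- Show replaced subjects alongside their replacements, with the reason for withdrawal.
- Report the proportion worsened with an exact 95% confidence interval.
- Keep the CS population as a supportive completer summary.

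The cost is a change of wording in Sections 14.2.3 and 14.5.4 and the matching tables. No visit or measurement is added. The drawback is that some last values will reflect less than 12 weeks of exposure, so duration of exposure should be shown beside them.
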